5.1.3 Prohibited Medications, Procedures, and Activities

Medication necessary for the health and well-being of the subject is permitted provided the subject has been at a stable dose for 30 days prior to screening/baseline visit. The use of any medication that could affect the course of acne is prohibited during the entire study period. Subjects should not apply creams, lotions, powders or any topical product other than the assigned treatment to the treatment area. See below Table 3: Restrictions and Prohibited Medications & also exclusion criteria.

[Redacted]

[Redacted]

[Redacted]

[Redacted]

[Redacted]

[Redacted]

[Redacted]

[Redacted]

[Redacted]

[Redacted]

[Redacted]

[Redacted]

[Redacted]

[Redacted]

[Redacted]

[Redacted]

[Redacted]

[Redacted]	[Redacted]	[Redacted]	[Redacted]	[Redacted]	[Redacted]	[Redacted]	[Redacted]	[Redacted]	[Redacted]	[Redacted]
[Redacted]	[Redacted]	[Redacted]	[Redacted]	[Redacted]	[Redacted]	[Redacted]	[Redacted]	[Redacted]	[Redacted]	[Redacted]
[Redacted]	[Redacted]	[Redacted]	[Redacted]	[Redacted]	[Redacted]	[Redacted]	[Redacted]	[Redacted]	[Redacted]	[Redacted]
[Redacted]	[Redacted]	[Redacted]	[Redacted]	[Redacted]	[Redacted]	[Redacted]	[Redacted]	[Redacted]	[Redacted]	[Redacted]
[Redacted]	[Redacted]	[Redacted]	[Redacted]	[Redacted]	[Redacted]	[Redacted]	[Redacted]	[Redacted]	[Redacted]	[Redacted]
[Redacted]	[Redacted]	[Redacted]	[Redacted]	[Redacted]	[Redacted]	[Redacted]	[Redacted]	[Redacted]	[Redacted]	[Redacted]
[Redacted]	[Redacted]	[Redacted]	[Redacted]	[Redacted]	[Redacted]	[Redacted]	[Redacted]	[Redacted]	[Redacted]	[Redacted]
[Redacted]	[Redacted]	[Redacted]	[Redacted]	[Redacted]	[Redacted]	[Redacted]	[Redacted]	[Redacted]	[Redacted]	[Redacted]

[Redacted text block]

[Redacted]	[Redacted]	[Redacted]	[Redacted]	[Redacted]	[Redacted]	[Redacted]	[Redacted]	[Redacted]
[Redacted]	[Redacted]	[Redacted]	[Redacted]	[Redacted]	[Redacted]	[Redacted]	[Redacted]	[Redacted]
[Redacted]	[Redacted]	[Redacted]	[Redacted]	[Redacted]	[Redacted]	[Redacted]	[Redacted]	[Redacted]
[Redacted]	[Redacted]	[Redacted]	[Redacted]	[Redacted]	[Redacted]	[Redacted]	[Redacted]	[Redacted]
[Redacted]	[Redacted]	[Redacted]	[Redacted]	[Redacted]	[Redacted]	[Redacted]	[Redacted]	[Redacted]
[Redacted]	[Redacted]	[Redacted]	[Redacted]	[Redacted]	[Redacted]	[Redacted]	[Redacted]	[Redacted]
[Redacted]	[Redacted]	[Redacted]	[Redacted]	[Redacted]	[Redacted]	[Redacted]	[Redacted]	[Redacted]
[Redacted]	[Redacted]	[Redacted]	[Redacted]	[Redacted]	[Redacted]	[Redacted]	[Redacted]	[Redacted]

Acceptable Medications for use throughout the study:

1. Contraceptives – Acceptable methods of birth control as listed in the Inclusion Criteria. Subjects on hormonal contraception must be stabilized on the same type for at least 3 months prior to enrollment in the study and must not change the method during the study.
2. Acetaminophen - Acetaminophen will be allowed during the study with a maximum dose of 1g (i.e., 1000 mg) twice daily and for a maximum of 3 consecutive days.
3. Non-medicated moisturizers (supplied by sponsor) or cleaning agents only, when necessary, as directed by investigator.
4. Oral retinoids, therapeutic vitamin A supplements of less than 10,000 units/day (multi-vitamins are allowed).

Subjects will be allowed to apply the study medication to any affected area(s) of their trunk as needed. No other medication will be allowed to be applied to these affected area(s).

Subjects will be questioned about all prescription and over the counter (OTC) concomitant medication use (including vitamins, nutritional supplements, herbal supplements, all topical products) at each study visit. All concomitant medications will be recorded in the Subject's source documents. Any Subject who violates the listed restrictions may be dropped from continued participation in the study by the discretion of investigator.

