- 4) Subjects with nodulocystic acne (> 2 nodules and cysts). [Nodules or cysts defined as; deep-seated in the skin (i.e., centered in the dermis or subcutis) and an inflammatory lesion greater than or equal to 5 mm in diameter], acne conglobata, acne fulminans, secondary acne (chloracne, drug-induced acne, etc.) or acne vulgaris requiring systemic treatment.

-
- 5) Subjects with excessive facial hair (e.g., beards, sideburns, moustaches, etc.) that would interfere with diagnosis or assessment of acne vulgaris.
 - 6) Subjects with tattoos or excessive facial scarring that, in the Investigator's opinion, may interfere with the evaluation of the patient's acne.
 - 7) Subjects who have used within 6 months prior to screening/baseline oral retinoids (e.g., Accutane[®]) or therapeutic vitamin A supplements of greater than 10,000 units/day (multivitamins are allowed). These treatments with oral retinoids or Vitamin A supplements are prohibited during the study participation.
 - 8) Subjects who have used within 1 month prior to screening/baseline neuromuscular blocking agents or androgen receptor blockers (e.g., spironolactone, Flutamide etc.).
 - 9) Subjects who have had laser therapy, electrodesiccation phototherapy and or cosmetic procedures (e.g., ClearLight[®] BOTOX, Filler, micro needling) to the facial area within 6 months prior to study entry.
 - 10) Subjects who have had facial cosmetic procedures (e.g., facials) or application of cosmetic products (cosmetics, makeup or facial products that have a strong drying or possible interactive effect, particularly preparations containing spices, lime sulfur, resorcinol, or salicylic acid with tretinoin or other retinoids) which may affect the efficacy and safety profile of the investigational product within 2 weeks prior to study entry.
 - 11) Subjects who have received radiation therapy and/or anti-neoplastic agents within 3 months prior to screening/baseline.
 - 12) Subjects who have used for less than (<) 3 months prior to screening/baseline estrogens or oral contraceptives; use of such therapy must remain constant throughout the study.
 - 13) Subjects who have used any of the following procedures on the face within 1 month prior to screening/baseline or use during the study:
 - a) cryodestruction or chemodestruction,
 - b) dermabrasion,
 - c) photodynamic therapy,
 - d) acne surgery,
 - e) intralesional steroids, or
 - f) X-ray therapy.

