5.1.2 Exclusion Criteria

- 1) Female Subjects who are pregnant, lactating or planning to become pregnant during study participation.
- 2) Subjects with a history of hypersensitivity or allergy to trifarotene, tretinoin, retinoids, or any of the study medication ingredients.
- 3) Subjects with the presence of any skin condition that would interfere with the diagnosis or assessment of acne vulgaris (Such conditions include but are not limited to the following on the face: rosacea, dermatitis, psoriasis, squamous cell carcinoma, eczema, acneiform eruptions caused by medications, steroid or corticosteroid-induced acne, steroid folliculitis, or bacterial folliculitis, auto-immune disease, perioral dermatitis, carcinoid syndrome, mastocytosis, or acneiform eruptions caused by make-up and medication, facial psoriasis and facial eczema).
- 4) Subjects with nodulocystic acne (> 2 nodules and cysts). [Nodules or cysts defined as; deep-seated in the skin (i.e., centered in the dermis or subcutis) and an inflammatory lesion greater than or equal to 5 mm in diameter], acne conglobata, acne fulminans, secondary acne (chloracne, drug-induced acne, etc.), or acne vulgaris requiring systemic treatment.
- 5) Subjects with excessive facial hair (e.g., beards, sideburns, moustaches, etc.) that would interfere with diagnosis or assessment of acne vulgaris.
- 6) Subjects with tattoos or excessive facial scarring that, in the Investigator's opinion, may interfere with the evaluation of the subject's acne.
- 7) Subjects who have used within 6 months prior to screening/baseline oral retinoids (e.g., Accutane[®]) or therapeutic vitamin A supplements of greater than 10,000 units/day (multivitamins are allowed). These treatments with oral retinoids or Vitamin A supplements are prohibited during the study participation.
- 8) Subjects who have used within 1 month prior to screening/baseline neuromuscular blocking agents or androgen receptor blockers (e.g., spironolactone, Flutamide etc.).
- 9) Subjects who have had laser therapy, electrodesiccation, phototherapy and or cosmetic procedures (e.g., ClearLight[®] BOTOX, Filler, micro needling) to the facial area within 6 months prior to study entry.

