5.1.5 Subject Disposition and Discontinuation

All Subjects are free to withdraw from participation in the study at any time, for any reason, specified or unspecified, and without prejudice to further treatment. The criteria for enrollment are to be followed explicitly. Investigators are urged to enroll only those eligible Subjects who are likely to complete the entire study and who are willing to comply with the protocol-specified procedures. It is the right and duty of the investigator to interrupt the treatment of any Subject whose health or well-being may be threatened by continuation in this study, or who may be experiencing unmanageable factors that may interfere with the study procedures and/or the interpretation of study results. Such Subjects should be withdrawn from the study rather than continued under a modified regimen. The reason for withdrawal or discontinuation from the study will be documented appropriately.

In addition, investigational product will be stopped, and Subjects will be discontinued from the study for any of the following reasons:

- a. If the Subject withdraws his or her consent/assent for any reason.
- b. Subjects who are discontinued early from the study due to lack of treatment effect should be included in the PP population as treatment failures, using Last Observation Carried Forward (LOCF).
- c. If the Subject's acne condition has worsened beyond grade 4 or to the degree that the Principal Investigator feels it is unsafe for the Subject to continue in the study, the subject should be discontinued, but included in the mITT and PP population analysis using LOCF and provided with effective rescue treatment for exacerbation of their acne.
- d. 
- e. If the Subject has a SAE.
- f. If the Subject's drug code is unblinded.
- g. If an adverse event occurs for which the Subject desires to discontinue treatment or the Principal Investigator determines that it is in the Subject's best interest to be discontinued.
- h. If there is a significant protocol deviation if it affects the safety or well-being of the subject.
- i. 
- j. If a concomitant therapy is reported or required which is liable to interfere with the results of the study.
- k. If the Subject is lost to follow-up.
- l. If the Subject becomes pregnant.
- m. If the Subject becomes a prisoner or becomes involuntarily incarcerated.
- n. Any other reason that may affect the outcome of the study or the safety of Subjects; or
- o. Termination of the study by the Sponsor.

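### The acceptable-medication list in Protocol 5.1.3 names oral retinoids, which exclusion 7 prohibits during the study

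*Protocol*

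**What the plan says.** Protocol 5.1.3 (Prohibited Medications, Procedures, and Activities) opens with a general rule: "The use of any medication that could affect the course of acne is prohibited during the entire study period". It then sends the reader to the table of restrictions, which is redacted in the public copy, and to the exclusion criteria: "See below Table 3: Restrictions and Prohibited Medications & also exclusion criteria".

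The same section closes with a list of medications that are acceptable for the whole study. Item 4 is "Oral retinoids, therapeutic vitamin A supplements of less than 10,000 units/day (multi-vitamins are allowed".

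Exclusion 7 appears in the synopsis and again in 5.1.2. It excludes subjects who used oral retinoids in the six months before screening/baseline, or "therapeutic vitamin A supplements of greater than 10,000 units/day (multivitamins are allowed". It ends: "These treatments with oral retinoids or Vitamin A supplements are prohibited during the study participation". Exclusion 14d also refers to the six-month washout for oral retinoids.

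**The concern.** The acceptable-medication list is an instruction that site staff can be expected to consult while subjects are on treatment. If it permits a drug that the exclusion criteria forbid, a site can follow the protocol and break it at the same time.

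The drug class matters here. The protocol itself treats oral retinoids as systemic acne treatment with a long washout. Use during the 12 weeks would affect the inflammatory and the non-inflammatory lesion counts, and so both co-primary endpoints. It would also add systemic retinoid exposure to a topical retinoid. A medication listed as acceptable might also not be recorded as a protocol deviation.

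**Working it through.** There is no figure to reproduce, so the check is a comparison of texts.

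1. **Status of the two statements.** Item 4 stands under a heading that makes it a permission for the whole study. The last sentence of exclusion 7 is a prohibition for the duration of participation. They cover the same period and the same drug class.

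2. **Possible readings of item 4.**
   - The dose limit applies only to vitamin A. Oral retinoids are then acceptable without limit.
   - The dose limit applies to both. Oral retinoids are then acceptable below 10,000 units/day.
   - The two phrases are in apposition, so that only low-dose vitamin A is meant. This fails, because oral retinoids are not low-dose vitamin A supplements and exclusion 7 names the two as separate treatments.

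   Exclusion 7 attaches no dose to oral retinoids, so each of the first two readings contradicts it.

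3. **The vitamin A part.** Exclusion 7 excludes doses above 10,000 units/day and item 4 accepts doses below 10,000. These agree except at exactly 10,000 units/day, which neither text covers.

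4. **Likely origin.** Item 4 has the same elements in the same order as exclusion 7 (oral retinoids, therapeutic vitamin A, the 10,000-unit threshold, the multivitamin allowance), with the inequality reversed. Reversing it turns the vitamin A exclusion into an allowance. Oral retinoids have no threshold to reverse and should have been dropped. This is an inference, but the wording supports it well.

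5. **Which other rules ban on-study use.** Inclusions 5 and 10 commit subjects to avoid other topical acne medications or antibiotics, not oral retinoids. Exclusion 14d bars systemic acne treatment during the study but sets oral retinoids apart, because of their longer washout. In the visible text, the last sentence of exclusion 7 is thus the only on-study ban that names oral retinoids, and it is the sentence that item 4 contradicts. The general ban in 5.1.3 covers them without naming them.

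6. **Redaction.** Item 4 and exclusion 7 are both fully legible. Whatever the redacted table in 5.1.3 says, it cannot make both true.

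**The case against.** The strongest reply is that the intent to prohibit is clear and that other rules would stop the drug being used:

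- The six-month washout in exclusion 7 keeps current users out, and exclusion 4 removes subjects with "acne vulgaris requiring systemic treatment".
- 5.1.3 points the reader back to the exclusion criteria. It also limits necessary medication to drugs at a stable dose for 30 days before baseline, which no eligible subject could satisfy for an oral retinoid.
- The discontinuation list in 5.1.5 is mandatory, and reason j reads "If a concomitant therapy is reported or required which is liable to interfere with the results of the study".
- Section 8.7 requires discontinuation when an adverse event calls for a prohibited medication.
- The redacted table may state the correct rule again.

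Most of this stands, and it is why actual exposure is unlikely. It does not remove the wrong permission. Section 8.7 depends on what counts as prohibited, which is the very thing item 4 blurs. Reason j needs a judgement that the therapy is liable to interfere, and a site could point to item 4 against that judgement. For breaches of the restrictions, 5.1.3 leaves the outcome open: "Any Subject who violates the listed restrictions may be dropped from continued participation in the study by the discretion of investigator".

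A further reply concerns the analysis populations. Subjects who worsen and need rescue therapy are discontinued and kept in mITT and PP by LOCF (Protocol 10.2, SAP 6.3). In the visible text of SAP 7.6.2, those who miss Week 12 for a reason other than lack of treatment effect leave PP. The visible text does not settle PP status for a subject who starts an oral retinoid, stays in the study and attends Week 12. However, the PP definition is largely redacted and may cover this case, so the point carries no weight here.

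**Conclusion.** The contradiction is real, and item 4 is wrong as written. It is a minor point, probably a drafting slip, in a rule that sites act on. No size can be derived: the documents give no rate of on-study oral retinoid use and no effect from which to calculate one. No change to sample size, alpha, power or the planned analysis is claimed. The conclusion rests only on the visible wording of item 4, exclusion 7 and the opening of 5.1.3. That it is a slip rather than an intended exception is an inference; no visible text provides such an exception.

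**What to change.** Delete the oral retinoids from item 4, so that it permits only vitamin A supplements of no more than 10,000 units/day, with multivitamins allowed. Writing the limit as no more than 10,000 makes it the exact complement of exclusion 7 and closes the gap at 10,000 itself.

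Send sites a short clarification that oral retinoid use during the study is prohibited and counts as a protocol deviation. Protocol 13.7 already requires deviations to be logged, so no new process is needed.

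The cost is a one-line protocol correction and a brief note to sites. Design and analysis are unchanged.

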5.1.4 Precautions

The following precautions are to be taken during this study:

1. To minimize exposure to sunlight and or extreme weather conditions, a wide-brimmed hat or other protective clothing should be worn. 
2. The IMP should not be applied to cuts, open wounds, abrasions, sunburn or eczematous skin.
3. The IMP should not be applied to the eyes, the mouth/lips, the angles/corners of the nose or any mucous membranes.
4. Subjects should wash their hands before and after application of the product.

If a reaction suggesting sensitivity or chemical irritation occurs, the Principal Investigator should assess the Subject's condition as soon as possible (i.e., during an Unscheduled Visit) and determine whether treatment should be discontinued. If a Subject is discontinued from the study during an Unscheduled Visit, the Unscheduled Visit will be referred to as an Early Discontinuation Visit and all procedures scheduled for the Early Discontinuation Visit will be performed.

5.1.5 Subject Disposition and Discontinuation

All Subjects are free to withdraw from participation in the study at any time, for any reason, specified or unspecified, and without prejudice to further treatment. The criteria for enrollment are to be followed explicitly. Investigators are urged to enroll only those eligible Subjects who are likely to complete the entire study and who are willing to comply with the protocol-specified procedures. It is the right and duty of the investigator to interrupt the treatment of any Subject whose health or well-being may be threatened by continuation in this study, or who may be experiencing unmanageable factors that may interfere with the study procedures and/or the interpretation of study results. Such Subjects should be withdrawn from the study rather than continued under a modified regimen. The reason for withdrawal or discontinuation from the study will be documented appropriately.

In addition, investigational product will be stopped, and Subjects will be discontinued from the study for any of the following reasons:

- a. If the Subject withdraws his or her consent/assent for any reason.
- b. Subjects who are discontinued early from the study due to lack of treatment effect should be included in the PP population as treatment failures, using Last Observation Carried Forward (LOCF).
- c. If the Subject's acne condition has worsened beyond grade 4 or to the degree that the Principal Investigator feels it is unsafe for the Subject to continue in the study, the subject should be discontinued, but included in the mITT and PP population analysis using LOCF and provided with effective rescue treatment for exacerbation of their acne.
- d. 
- e. If the Subject has a SAE.
- f. If the Subject's drug code is unblinded.
- g. If an adverse event occurs for which the Subject desires to discontinue treatment or the Principal Investigator determines that it is in the Subject's best interest to be discontinued.
- h. If there is a significant protocol deviation if it affects the safety or well-being of the subject.
- i. 
- j. If a concomitant therapy is reported or required which is liable to interfere with the results of the study.
- k. If the Subject is lost to follow-up.
- l. If the Subject becomes pregnant.
- m. If the Subject becomes a prisoner or becomes involuntarily incarcerated.
- n. Any other reason that may affect the outcome of the study or the safety of Subjects; or
- o. Termination of the study by the Sponsor.

Subjects who withdraw from the study early will have Early Discontinuation procedures performed. Subjects who withdraw from the study will not be replaced. All subjects who are randomized will be included in the safety monitoring tabulating all adverse events experienced after dosing.

A significant or major protocol deviation is defined as any subject or Investigator activity that could have possibly interfered with the therapeutic administration of the treatment, safety or well-being of the subject or the precise evaluation of treatment efficacy such as may affect data integrity. Subjects with protocol deviations are not required to be discontinued from the study unless, in the Investigator's opinion, continuation in the study could be harmful to the health or wellbeing of the subject. Subjects that have a major protocol deviation which effects their safety or wellbeing should be discontinued.

The reasons for a Subject discontinuation will be documented. If a Subject is discontinued from the study for any reason, Early Discontinuation Visit procedures will be completed and any outstanding data and study drug should be collected if possible. In addition to the reason for discontinuation the collected data will include the initiation of any rescue medicines, the date of removal and will be documented in the electronic Case Report Form (eCRF). The Sponsor will be notified.

Before a subject is considered to be lost to follow-up, the Principal Investigator will document all attempts to reach the Subject twice by telephone and will send a certified follow-up letter.

In the event that a subject discontinues from the study at any time due to an adverse event (AE), the reason for discontinuation, the nature of the event and its clinical course must be fully documented (see also reporting AEs and SAES, Section 11.0). For such a subject, the Principal Investigator must strive to follow the subject until the adverse event has resolved, becomes clinically insignificant, is stabilized or the subject is lost to follow-up. In case of any serious adverse events, procedures for reporting must be followed.

6 SAFETY AND TOLERABILITY EVALUATIONS

Safety will be assessed based on following:

- Vital signs evaluation,
- Physical Examination
- COVID-19 symptoms screening,
- Reported Adverse Events and Serious Adverse Events,
- Assessment of local facial tolerability-rating of erythema, dryness, stinging/burning, erosion, edema, pain and itching for each treatment group will be recorded and reported,
- Lack of effect of investigative products on indication.

